3.4.2 Secondary Study Hypotheses

The secondary study hypotheses that will be tested in IQOS users and smokers are:

1. That there will be favorable changes of PD at 3 months in IQOS users as compared to smokers who continue to smoke cigarettes in patients with generalized chronic periodontitis.
2. That there will be favorable changes of CAL at 3 and 6 months in IQOS users as compared to smokers who continue to smoke cigarettes in patients with generalized chronic periodontitis.
3. That there will be favorable changes at 3 and 6 months in total NNAL and CEMA levels in IQOS users as compared to smokers who continue to smoke cigarettes

Confidentiality Statement

Data and information contained in this document are considered to constitute trade secrets and confidential commercial information, and the legal protections provided to such trade secrets and confidential information are hereby claimed under the provisions of applicable law. No part of this document may be publicly disclosed without the written consent of Philip Morris Products S.A

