5.3.3 Change from baseline

Mean change from Baseline is the mean of all individual patients' change from Baseline values. Each individual change from Baseline will be calculated by subtracting the individual patient's Baseline value from the value at a given timepoint.

For log-transformed variables, the geometric relative change (RC) from baseline will be calculated,

$$\text{RC} = 100 * (\exp(\text{mean}(\ln(x) - \ln(\text{base}))) - 1)$$

Where $\ln(x)$ is the natural logarithm of the observation and $\ln(\text{base})$ is the natural logarithm

Confidentiality Statement

Data and information contained in this document are considered to constitute trade secrets and confidential commercial information, and the legal protections provided to such trade secrets and confidential information are hereby claimed under the provisions of applicable law. No part of this document may be publicly disclosed without the written consent of Philip Morris Products S.A

of the baseline value.

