9.1.8 Multiple Comparison/Multiplicity

There will be an adjustment for multiplicity for the secondary testing of CAL and PD within the As Exposed Set, as well as for BoExp. PD at 3 months and CAL at 6 and 3 months will be tested in a hierarchical manner, depending on the outcome of the test at previously specified endpoint in hierarchical testing order. The order of testing is as follows,

The primary analysis, of PD at 6 months will be tested using a one-sided alpha level of 2.5%.

1. PD at 6 months will be tested.

The secondary analysis of PD at 3 months and CAL at 6 and 3 months will be tested in a hierarchical manner, using a one-sided alpha level of 2.5%, depending on the outcome of the test at previously specified endpoint in hierarchical testing order.

1. PD at 3 months will be tested only if the test for PD at 6 months is significant.

2. CAL at 6 months will be tested only if the test for PD at 3 months is significant

3. CAL at 3 months will be tested only if the test for CAL at 6 months is significant.

Additional secondary analysis of the BoExp will be tested, in a hierarchical manner within each BoExp (independent of the other statistical tests being performed), using a one-sided alpha level of 2.5%. The hierarchical order will be:

1. BoExp at 6 months will be tested.

2. BoExp at 3 months will be tested only if the test for BoExp at 6 months is significant.

Total NNAL and CEMA levels (concentration data adjusted for creatinine), analyzed on a logarithmic scale, will be tested at 6 and then 3 months, in that order, so that the testing of each BoExp will stop if the test is not significant.

Confidentiality Statement

Data and information contained in this document are considered to constitute trade secrets and confidential commercial information, and the legal protections provided to such trade secrets and confidential information are hereby claimed under the provisions of applicable law. No part of this document may be publicly disclosed without the written consent of Philip Morris Products S.A

Unless stated otherwise, all statistical tests will be one-sided and conducted at the 2.5% level, and all CIs will be two-sided 95%.

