4. Perform a likelihood ratio test and drop the covariate with the largest p-value for the likelihood ratio statistic if it is more than 0.05.
5. Repeat steps 2 and 3 until no more covariates can be dropped.
6. Refit the final model with the covariates remaining in the model and estimate PD for each product use group using the restricted likelihood method.

Note that other covariates may be added if deemed necessary.

Number of subjects included in analysis, regression coefficients, 95% CI for regression coefficient, p-value for regression coefficient, Least Squares (LS) means (Cigarette User, IQOS User and Dual-User categories), Difference in LS Means (Cigarette User vs IQOS User/Dual-User) and 95% CI for Difference in LS Means will be presented.

The model fit will be assessed by the analysis of the residual (diagnostics) and by comparing the values predicted vs. the observed values (calibration).

Confidentiality Statement

Data and information contained in this document are considered to constitute trade secrets and confidential commercial information, and the legal protections provided to such trade secrets and confidential information are hereby claimed under the provisions of applicable law. No part of this document may be publicly disclosed without the written consent of Philip Morris Products S.A

Primary Analysis of Change from Baseline in PD at V4	
	The residuals, predicted vs observed values from the final model will be plotted.
Target visit	: V4 (6 Months)
Sample code	
ODS GRAPHICS ON;
 
PROC MIXED DATA = X METHOD=ML (REML for final model);
 
CLASS Product_use Subject Visit site;
 
MODEL PD reduction (Dependent variable) = avisit avisit*trt01a 3 4 5 6 7 8 9 10 11 12/ ddfm=kr outp=dsn residuals vciry;
 
RANDOM Site;
 
REPEATED / subject=visit (subject) type=toep;
 
LSMEANS Product_use * Visit / CL ALPHA=0.025 DIFF E UPPER;
 
RUN;
 
Where 1 2 3 4 5 6 7 8 9 10 11 12 refers to the covariates.
 
ODS GRAPHICS OFF;

Output	
15.4.5.1 Primary Analysis of Change from Baseline in Pocket Depth (mm) at V4 with Initial Pocket Depth \geq 4 mm - As Exposed Set -
 
15.4.5.2 Regression Coefficients and Graphical Diagnostics of Primary Analysis of Change from Baseline in Pocket Depth (mm) at V4 - As Exposed Set -
 
15.4.5.3 Primary Analysis of Change from Baseline in Pocket Depth (mm) at V4: Variables Dropped - As Exposed Set -

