	
15.4.7.4 Regression Coefficients and Graphical Diagnostics of Analysis of Change from Baseline in Clinical Attachment Level (mm) - As Exposed Set -
 
15.4.7.17 Analysis of Change from Baseline in Pocket Depth (mm) at V3: Variables Dropped - As Exposed Set -
 
15.4.7.18 Analysis of Change from Baseline in Clinical Attachment Level (mm): Variables Dropped - As Exposed Set -

--	---

Summary Table of Analysis for BoExp Geometric mean value

Population	:	
 As Exposed Set
Contents	:	
The analysis will be performed on the As Exposed Set using a mixed model for repeated measurements (MMRM).
 
The model will include the change from baseline of log transformed BoExp adjusted for creatinine as the dependent variable, adjusting for the following covariates;
 
 Daily cigarette consumption Sex Visit Baseline level of BoExp Product use Interaction between visit and product use Interaction between Daily cigarette consumption at V1 and product use Average daily cigarette use at each visit 
Site will be included as a random effect.
 
For analysis, PROC MIXED will be used. Site will be included as RANDOM effect.
 
Degree of freedom will be adjusted by using KR.
 
Number of patients included in analysis, regression coefficient, 95% CI for regression coefficient, p-value for regression coefficient,

Confidentiality Statement

Data and information contained in this document are considered to constitute trade secrets and confidential commercial information, and the legal protections provided to such trade secrets and confidential information are hereby claimed under the provisions of applicable law. No part of this document may be publicly disclosed without the written consent of Philip Morris Products S.A

Summary Table of Analysis for BoExp Geometric mean value	
	
Geometric LS means (IQOS-cigarette), Ratio of Geometric LS Means and 95% CI for Ratio of Geometric LS means at 3 and 6 month for each product use will be presented.
 
The modelling assumptions will be evaluated and the model fit will be assessed by the analysis of the residual (diagnostics) and by comparing the values predicted vs. the observed values (calibration).
 
 • Predicted value and observed value will be plotted.

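### The NNAL and CEMA tests inherit an upper-tailed code line written for pocket depth reduction; on the biomarker table's own IQOS-minus-cigarette scale that tail is the wrong one, and no single tail and order fits both outcomes as labelled

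*SAP*

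**What the plan says.** **Hypothesis and testing rule.** SAP 3.4.2 expects "That there will be favorable changes at 3 and 6 months in total NNAL and CEMA levels in IQOS users" relative to continuing smokers. SAP 9.1.8 makes this a formal test: "Additional secondary analysis of the BoExp will be tested, in a hierarchical manner within each BoExp", with 6 months first and 3 months only if the 6-month test succeeds. The general rule there is "Unless stated otherwise, all statistical tests will be one-sided and conducted at the 2.5% level, and all CIs will be two-sided 95" per cent. Neither section says which tail applies to the biomarkers (BoExp).

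**Biomarker model.** SAP 9.5.2.1 states: "The model will include the change from baseline of log transformed BoExp adjusted for creatinine as the dependent variable". SAP 5.3.3, in the urinary biomarker part, forms each change by subtracting the "Baseline value from the value at a given timepoint". The results to be shown are "Geometric LS means (IQOS-cigarette), Ratio of Geometric LS Means and 95% CI for Ratio of Geometric LS means at 3 and 6 month". The sample-code row refers the analyst to the primary analysis, and the FAS and Per Protocol biomarker table in 9.5.2.2 does the same.

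**Primary code.** The code in SAP 9.5.1.1 labels its outcome "PD reduction (Dependent variable" and closes its LSMEANS line with "CL ALPHA=0.025 DIFF E UPPER". Protocol 12.2 writes out a null and alternative only for pocket depth (PD) at 6 months. There, change is baseline minus endline and the alternative is IQOS minus cigarette above zero.

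**Contrast order.** The text around the primary code describes the comparison as cigarette user against IQOS user, and the biomarker remarks in 9.5.2.1 also name cigarettes first.

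**The concern.** A one-sided test needs a direction. The only direction written anywhere in the SAP is the upper tail in the primary code, and that code was built for an outcome where a larger value is better. NNAL and CEMA improve by falling. Protocol 2.1 describes reductions in exposure markers with IQOS, and Protocol 4.1 gives reduced exposure as the design aim.

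If the biomarker program takes over the upper tail and uses the IQOS-minus-cigarette order of its own table, it tests for a rise. A true reduction would then give a p-value near 1, the 6-month test would fail, and the 3-month test for that marker would be closed. The p-value would also contradict the reported confidence interval.

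**Working it through.** **1. The plan's own figure.** Protocol 12.2 gives one-sided alpha 2.5%, power 80%, SD 0.5 and difference 0.25 mm. The normal formula gives n = 2 × (1.960 + 0.842)² × 0.5²/0.25² = 62.8, so 63 per arm; the t-based solution is 63.8, so 64. Then 64/0.75 = 85.3, so 86 per arm and 172 in total. The stated 64, 86 and 172 are reproduced. They concern PD; the documents give no power or sample size for the biomarkers.

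**2. Which tail is favourable.**

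| Outcome and coding | Sign of benefit, IQOS − cigarette | Sign of benefit, cigarette − IQOS |
|---|---|---|
| PD, baseline minus endline (code label, Protocol 12.2) | positive: UPPER right | negative: UPPER wrong |
| log BoExp, value minus baseline (SAP 5.3.3) | negative: UPPER wrong | positive: UPPER right |

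In each column UPPER is right for one row and wrong for the other. Swapping the order only moves the error from one outcome to the other.

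**3. Rejection probability on the IQOS-minus-cigarette scale.** Let d = ln(1 − fall), s = √ln(1 + CV²) and se = s√(2/n).
- Upper tail: Φ(d/se − 1.96).
- Lower (favourable) tail: Φ(−d/se − 1.96).

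With no difference, d = 0 and both equal 2.5%. For any fall, d < 0, so the upper-tail probability is below 2.5% whatever the SD or group size. This needs no assumed effect.

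To show how far below, the following are assumed because the documents do not give them: CV 50%, 100% or 150% (s = 0.472, 0.833 or 1.086) and 40 or 64 per exposure group.

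Worked case, n = 64, CV 100%, fall 30%: se = 0.833 × √(2/64) = 0.147; d = −0.357; d/se = −2.42. Lower tail Φ(0.46) = 0.68; upper tail Φ(−4.38) = 0.000006.

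| n per group | CV | True fall | Lower tail | Upper tail |
|---|---|---|---|---|
| 64 | 50% | 30% | 0.990 | 2.3e-10 |
| 64 | 100% | 5% | 0.054 | 0.0105 |
| 64 | 100% | 20% | 0.329 | 0.00025 |
| 64 | 100% | 30% | 0.679 | 5.8e-6 |
| 64 | 100% | 50% | 0.997 | 1.3e-11 |
| 64 | 150% | 50% | 0.951 | 1.3e-8 |
| 40 | 150% | 5% | 0.040 | 0.0150 |
| 40 | 150% | 20% | 0.149 | 0.0020 |

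Over the whole assumed grid, the upper tail rejects at most 1.5% of the time for a 5% fall and 0.2% for a 20% fall.

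**4. Gate.** The 3-month test is reached only after rejection at 6 months, so its chance of success cannot exceed the upper-tail figures above.

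**The case against.** The strongest reply is that the code does not fix the order of subtraction, and the text beside it puts cigarette first. If the difference is cigarette minus IQOS, UPPER is the correct tail for a fall in NNAL or CEMA. SAP 9.5.1.1 also calls the dependent variable the PD change from baseline, and the wording of 5.3.3 is general. If PD were also taken as value minus baseline, one UPPER line with cigarette minus IQOS would serve both outcomes. The bracketed order in the biomarker table may describe reported output rather than the tested difference.

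This much stands: the direction of the error is not settled. A reader might infer that the plan definitely tests whether IQOS raises the toxicant markers, that it will almost never find a reduction, and that a product raising them would be declared successful. The documents do not support that as a certainty, because it depends on one of two written orders. But the reading that rescues the shared line must override the outcome label in the code, the sign and order in Protocol 12.2, and the order in the biomarker table. Nothing in the SAP tells the analyst to do so.

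Other points also stand. This is sample code with placeholders, and the biomarker program must be adapted in any case. The word favourable makes the intent clear. The two-sided 95% CI for the ratio is reported regardless and would show the direction. The biomarker hierarchy is separate from the PD tests, so the primary evaluation criterion is not affected through this route.

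**Conclusion.** Wrong as written, with a conditional consequence. The firm finding is a conflict: the SAP gives one tail for two outcomes that, as labelled, improve in opposite directions, and it writes the contrast in both orders. On the biomarker table's own order, the one-sided test of total NNAL and CEMA cannot reject more than 2.5% of the time when the marker truly falls, and the 3-month test closes with it. On the other order, the biomarker test is right and the tail is wrong for PD reduction.

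The size of the power loss rests on the IQOS-minus-cigarette order and on assumed CVs, falls and group sizes. In particular, 64 is the PD figure, not a planned biomarker group size, and the as-exposed analysis also has a dual-user group. The power figures illustrate what a wrong tail does; they do not show which order the analyst would use. The reported CI and the clear intent limit the harm, so this should be corrected but does not by itself undermine the trial's main conclusion.

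**What to change.** In SAP 9.5.2.1 and 9.5.2.2, replace the biomarker reference to the primary code with a separate specification:
- Contrast: ln(IQOS/cigarette) for creatinine-adjusted total NNAL and CEMA.
- H0: contrast ≥ 0; HA: contrast < 0.
- Test: lower tail at 2.5%, which is equivalent to the upper limit of the two-sided 95% CI for the ratio lying below 1.

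NEQ is modelled with the same code but is not among the markers named for testing in SAP 3.4.2 or 9.1.8, so it can be reported with its CI alone.

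In SAP 9.5.1.1, state the sign of PD change and the order of the contrast so that they match Protocol 12.2: baseline minus endline, IQOS minus cigarette, upper tail.

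The cost is a sentence of wording and one code option for the biomarkers, plus a line of clarification for PD. No data or sample size changes. The direction should be fixed before anyone sees the biomarker results by group.
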